### *Implantation trephine (external and internal trephines)*

If judged necessary, the IMP ALLOB® (i.e., same syringe) can be administered into the delayed-union site from two different surgical approaches, using the same procedure.

**ALLOB-DU1 - Clinical Study Protocol**

ALLOB-DU1\_CSP

V 05

Author: [name]

February 02, 2017

Pg. 64/136

**5.3 Peri-operative antibiotic therapy and other medication**

All patients will receive a single intravenous infusion of cefazolin (2g) or any standard-of-care antibiotic therapy used at the investigating site at induction. Besides, drugs used during anaesthesia will not be systematically recorded in the CRF, except if an Adverse Event should have occurred.

Patients will be hospitalized for 24 or 48 hours, upon Investigator's judgement ( [REDACTED] [REDACTED] ). If patients are hospitalized for 24 hours, they must return to the Investigating Site for the Visit #2 – 48h post-implantation visit.

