**Study Endpoints and Criteria for Evaluation****Safety Criteria**

In addition to standard pharmacovigilance requirements, particular attention will be given to AE suggesting immune-mediated reactions, such as: general discomfort, uneasiness, ill feeling, pain or swelling in the implanted area, fever and any inflammatory reactions, flu-like symptoms (e.g., chills, body aches, shortness of breath, cutaneous rashes...). All severe AEs potentially related to the IMP and in particular those potentially related to the allogeneic reactions will be managed by the SMC who will analyse and report these events in a timely manner consistent with the safety of patient recruitment scheme.

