**ALLOB-DU1 - Clinical Study Protocol**

ALLOB-DU1_CSP	V 05	Author: [name]	February 02, 2017	Pg. 27/136
---------------	------	-------------	-------------------	------------

vascular diseases are well documented to increase risks of delayed- or non-union (Schmitz, 1999; Gaston, 2007). The use of non-steroidal anti-inflammatory drugs or corticosteroids can also inhibit bone healing (Giannoudis *et al.*, 2000), as well as the nutritional status of the patient and compliance with the post-operative regime (Gaston and Simpson, 2007).

Finally, prompt and appropriate treatment is needed because iatrogenic injury to the soft tissue envelope (i.e., excessive periosteal stripping), distraction across the fracture site, inadequate immobilization or fixation, can promote the development of delayed/non-union (Gaston and Simpson, 2007).

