## ALLOB-DU1 - Clinical Study Protocol

ALLOB-DU1_CSP	V 05	Author: [name]	February 02, 2017	Pg. 78/136
---------------	------	-------------	-------------------	------------

reactions. The causality assessment given by the Investigator should not be downgraded by the Sponsor. If the Sponsor disagrees with the Investigator's causality assessment, both, the opinion of the Investigator and the Sponsor should be provided with the report.

Determination of the causal relationship between an AE/SAE and the trial medication must be made by the Investigator by answering the question: "Is the causal relationship between the medicinal product and this AE/SAE reasonably possible?" on the following basis

- Yes: Certain
- Likely
- Unlikely
- No: Not related
- Unknown/ Not assessable

Indeed, causality assessment is a clinical decision based on all available information at the time of and after the occurrence of the event. The factors which may be considered when evaluating the causal relationship of an AE/SAE to the IMP administration include the followings:

- Underlying, concomitant, and/or intercurrent disease(s): each report should be evaluated in the context of the natural history and course of the disease being treated and any other diseases the patient may have had prior to, or developed during the course of the study
- Concomitant medication or treatment: other drugs the patient is taking or treatment the patient is receiving at the time of the event should be examined to determine whether any of them may be recognized to cause the event in question
- Known response pattern for this class of drug
- The pharmacology and pharmacokinetic of the IMP: absorption, distribution, metabolism, and excretion of the IMP or other medications the patient is receiving coupled with the pharmacodynamic responses should be considered when evaluating an event

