#### *10.5.2.5 Previous and concomitant medications*

Previous and concomitant medications will be summarised for the safety population.

Frequency of medication will be summarised using descriptive statistics:

- frequency of patients with at least one previous medication
- frequency of patients with at least one concomitant medication

Frequency will be given by ATC term according to the WHO Drug Dictionary (WHO DD) (last available version) used for drugs coding. Each frequency table will be sorted by descending frequency of ATC term and then within each ATC by descending frequency of WHO Drug name (all treatment groups).

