#### *10.5.4 Implantation procedure*

The whole procedures used for ALLOB® implantation will be summarized descriptively on the all enrolled patients.

These procedures concern:

- If the patient was able to undergo the implantation procedure;
- If the patient had any changes in health occurred since the last visit before implantation;
- If the IMP was released by the sponsor, the pharmacist or the investigator;
- If the implantation was performed;
- the duration of implantation operation;
- In case of a non-implantation, the reasons ;
- The prescribed dose,
- The administered dose and the reason if the prescribed dose was not totally administered;
- If fluoroscopy images were taken;
- If the IMP implantation was performed by the use of 2 different surgical approaches and if yes, the description of the 2 approaches;
- If operative blood loss with the description of the amount;
- Type of anaesthesia;
- Any relevant peri-procedural events.

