## ALLOB-DU1 - Clinical Study Protocol

ALLOB-DU1_CSP	V 05	Author: [name]	February 02, 2017	Pg. 99/136
---------------	------	-------------	-------------------	------------

During the 24 hours post-administration follow-up, number of patients having experienced AE/SAE or having done any changes in the concomitant medications will be described.

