## ALLOB-DU1 - Clinical Study Protocol

ALLOB-DU1\_CSP

V 05

Author: [name]

February 02, 2017

Pg. 108/136

Source documents may include, but are not limited to, a patient's medical records, hospital charts if any, clinic charts if any, the Investigator's patient study files, pharmacy dispensing records, recorded data from automated instruments, as well as the results of diagnostic tests, such as radiographs, laboratory and urine pregnancy tests.

The following information should be entered into the patient's medical record:

- Patient name, surname and date of birth
- Patient's contact information
- Medical chart (e.g. hospital source document tracking number), if any
- A statement that ICF was obtained with the date of ICF collection and a documentation on the person who conducted the Informed Consent discussion
- Dates of initial screening and all patient visits
- The patient identification number
- The study title and/or the protocol number and the name of the Sponsor
- Medical/surgical history and physical examination
- Results of blood pressure, heart rate, respiratory rate and body temperature
- Results of urine pregnancy tests (only for female with childbearing potential)
- Results of radiographs and CT Scan
- Laboratory results reports
- All concomitant medications and concurrent procedures (list of all prescription and non-prescription medications being taken at the time of entry/screening of the study. At each subsequent visit, changes to the list of medications will be recorded.)
- Occurrence and status of any AE and SAE
- The date the patient exited the study, and a notation as to whether the patient completed the study or the reason for discontinuation

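### Drugs given during anaesthesia are required in the CRF only when an adverse event occurs, so recording of an exposure depends on the outcome

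*Combined protocol and SAP*

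**What the plan says.** Section 5.3 requires a peri-operative antibiotic for all patients and then turns to other drugs: "drugs used during anaesthesia will not be systematically recorded in the CRF, except if an Adverse Event should have occurred". It does not say which AEs trigger recording, or within what time.

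Other parts of the protocol bear on the same data:

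- Section 10.5.2.5: "Previous and concomitant medications will be summarised for the safety population". No exception is stated for drugs given during anaesthesia.
- Section 10.5.4 lists what will be summarised about the implantation. It includes "Type of anaesthesia" but no anaesthetic or adjunct drugs. For the 24 hours after administration, the "number of patients having experienced AE/SAE or having done any changes in the concomitant medications will be described".
- Section 8.1.2, on judging causality: "other drugs the patient is taking or treatment the patient is receiving at the time of the event should be examined".
- Section 11.2, on the medical record: concomitant medications are listed at entry, and "At each subsequent visit, changes to the list of medications will be recorded".
- Synopsis, Safety Criteria: "particular attention will be given to AE suggesting immune-mediated reactions". Fever, rashes and swelling at the implanted area are among the examples.
- Section 8.2.2, Table 10, lists allergy and anaphylactic shock among the serious risks of anaesthesia.
- Section 1.1.4: "The use of non-steroidal anti-inflammatory drugs or corticosteroids can also inhibit bone healing".

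**The concern.** If an exposure is written down only when the outcome occurs, the data cannot describe how the two are related. Patients who received a drug and had no event are the group needed for comparison, and the rule does not ask for them. An absent entry could mean that the drug was not given, or that it was given and nothing happened.

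Two things are at stake. The first is the medication table. It is reported for the whole safety population, but for these drugs it would be filled mainly from patients with an AE. The second is the reading of early reactions. The reactions of most interest for an allogeneic cell product overlap clinically with reactions to anaesthetic drugs, and both can arise in the same hours. The trial has no control arm, so even a rough comparison of users and non-users of a given drug would be useful context. Corticosteroids and NSAIDs also bear on healing by the protocol's own account, although the documents say nothing about the effect of a dose given in theatre.

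**Working it through.** The plan states no figure on this point, so there is none to reproduce. The check is a reading of the recording rules followed by an illustration.

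**Reading the rules together.** Section 5.3 ties CRF entry to an AE. Section 10.5.4 names the type of anaesthesia but no drugs. The 24-hour summary covers changes in concomitant medication after administration, whether or not an AE occurred, so the gap is confined to the anaesthesia itself. Section 8.3.1.1 requires drugs used to treat an AE to be entered, but these again exist only where there is an AE. Section 11.2 places concomitant medications in the medical record. Section 11.3 verifies the CRF against source, which would not add an item that the CRF does not request. No visible text therefore requires these drugs in the CRF for patients without an AE. The Visit #2 procedure list is redacted, and nothing is inferred from it.

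**Illustration.** Inputs:

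- N = 32 treated patients, the maximum in the Synopsis.
- u = 0.50, the true share receiving a given drug (assumption).
- a = 0.30, 0.50 or 0.70, the share with an AE that triggers recording (assumption). A value of 0.10 is added in case only AEs close to the anaesthesia count.
- The drug has no effect on AEs, and the rule is applied strictly (assumptions).

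Formulas:

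- True users = N × u = 32 × 0.50 = 16.
- Recorded users = N × u × a = 16a; unrecorded users = 16(1 − a).
- Apparent use = u × a = 0.50a.
- AE rate among recorded users = 100%, because an AE is the condition for recording.
- AE rate among patients with no record = a(1 − u) / (1 − ua) = 0.50a / (1 − 0.50a).

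| a | Recorded users | Unrecorded users | Apparent use (true 50%) | AE rate, recorded users | AE rate, no record |
|---|---|---|---|---|---|
| 0.10 | 1.6 | 14.4 | 5% | 100% | 0.05/0.95 = 5.3% |
| 0.30 | 4.8 | 11.2 | 15% | 100% | 0.15/0.85 = 17.6% |
| 0.50 | 8.0 | 8.0 | 25% | 100% | 0.25/0.75 = 33.3% |
| 0.70 | 11.2 | 4.8 | 35% | 100% | 0.35/0.65 = 53.8% |

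The recorded fraction of users equals a, whatever the true use. With u from 0.25 to 0.75 and a from 0.10 to 0.50, the number of unrecorded users runs from 32 × 0.25 × 0.50 = 4.0 to 32 × 0.75 × 0.90 = 21.6. In every row a drug with no effect appears strongly associated with AEs.

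**The case against.** The strongest reply is that little follows from the gap. The data exist at source and can be retrieved. The wording does not forbid an entry without an AE. Causality is judged case by case, and in those cases the drugs are recorded; the SAE form (section 8.3.1.2) also captures concomitant drugs and the relationship to anaesthesia. The visible text plans no AE-by-drug analysis, and section 10.5.7 calls the safety analysis mainly descriptive. Section 10 defers detail to a SAP, and a footnote could state the limits of the medication table.

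Much of this stands, and it rules out several stronger readings:

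- A reader might infer that use of these drugs is lost altogether. It is absent from the CRF and dataset unless an AE occurs, but section 11.2 foresees a source record.
- A reader might infer that a safety block could be released because steroid or antihistamine cover hid a reaction. The documents mention no such cover and give no use rate or masking effect. The release rule in section 10.9 counts only grave SAEs possibly due to the product, so fever or rash would not ordinarily enter it. The block decision is not shown to be compromised.
- A reader might infer that full recording would separate product reactions from anaesthetic reactions. Every treated patient receives both the cells and an anaesthetic, in a single arm, so it would help but not settle attribution.
- A reader might count the antibiotic as part of the gap. Section 5.3 requires it for everyone in a separate sentence, so it is not.

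These points do not remove the outcome-dependent recording. A footnote would make the table honest but would not supply the missing users.

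**Conclusion.** The point holds as a data-collection flaw of limited reach. As section 5.3 is written, CRF capture of drugs used during anaesthesia depends on an AE having occurred. The 10.5.2.5 frequencies would under-count these drugs and link them artificially to AEs, and users and non-users of a given drug could not be compared.

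Under the stated assumptions (50% use, no effect on AEs, strict application), apparent use would be 15% to 35% for AE rates of 30% to 70%, and lower still if only peri-operative AEs trigger recording. The size depends on use and AE rates that the documents do not give. The 100% AE rate among recorded users describes the rule as written, since sites may enter drugs voluntarily. No effect on the primary efficacy endpoint, the interim rule or any planned test is shown. The case for change is that safety is part of the primary objective, immune-type reactions are its stated focus, and the remedy is cheap.

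**What to change.** Replace the sentence in section 5.3 with a rule along these lines: systemic drugs given during anaesthesia, at least corticosteroids, NSAIDs and antihistamines, are transcribed from the anaesthesia record into the CRF for every treated patient, whether or not an AE occurs. State in section 10.5.2.5 that these drugs are included in the medication summary.

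The cost is about one extra CRF page per patient, with its source verification, for at most 32 patients. For patients already treated, the same items could be taken from the source records where available. The change concerns recording only; no drug is required, restricted or altered.

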**5.4 Post-operative Management**

Following the implantation procedure and the hospital stay, immobilization and unloading of the treated bone will be requested and all patients will remain non-weight-bearing on the operated limb as long as judged necessary by the Investigator. Progressive mobilization and load bearing will be allowed thereafter.

[REDACTED] (at Visit #3).

**5.5 Revision Procedure during the Trial**

Simple osteosynthesis revision (defined as second intervention anywhere but at the fracture site) can be performed in case of osteosynthesis material instability as from Month 3 after treatment.

**5.6 Rescue Surgery Procedure**

Rescue surgery (when judged necessary, as from Month 3 after treatment) will be performed according to standard-of-care procedure of the investigating site.

## **ALLOB-DU1 - Clinical Study Protocol**

ALLOB-DU1 CSP

V 05

Author: [name]

February 02, 2017

Pg. 65/136

5.7

A large number of horizontal black bars of varying lengths, likely representing redacted text or data. The bars are arranged in a grid-like pattern, with some bars being significantly longer than others, creating a visual representation of data that has been obscured for privacy or security reasons.

## **ALLOB-DU1 - Clinical Study Protocol**

ALLOB-DU1 CSP

V 05

Author: [name]

February 02, 2017

Pg. 66/136

## **ALLOB-DU1 - Clinical Study Protocol**

## ALLOB-DU1 CSP

V 05

Author: [name]

February 02, 2017

Pg. 67/136

## 6 INVESTIGATIONAL PRODUCT

## 6.1 Investigational Medicinal Product

**Table 4: Characteristics of the Investigational Medicinal Product**

### ***Treatment administered***

The ALLOB® dose to be used in this study will depend upon the size of fracture interline and the surgical approach (from [REDACTED] at a concentration of [REDACTED] cells/ml). Therefore, ALLOB® volume will be determined on a case-by case basis.

## **ALLOB-DU1 - Clinical Study Protocol**

ALLOB-DU1 CSP

V 05

Author: [name]

February 02, 2017

Pg. 68/136

**Table 5: Administration of the Test Product**

	ALLOB® Product Procedure
Product	ALLOB®
Procedure/Route of administration	Percutaneous administration via a trephine
Single dose	████████ cells/ml (█████ depending on the delayed-union size)
Dosage schedule	1 single dose per subject at implantation visit (#2)

Regarding the packaging, labelling, shipment of the Investigational Medicinal Product (IMP), Standard Operating Procedures, including step-by-step instructions and detailed descriptions, will be provided to the Principal Investigator before the beginning of the trial. Complete information will be provided in the Study Procedure Manual and training of the healthcare professionals involved will also be conducted during the Site Initiation Visits and at the Investigator's Meeting.

6.2

A series of seven horizontal black bars of varying lengths, decreasing in length from left to right. The bars are positioned in a horizontal line, with the first bar being the longest and the seventh bar being the shortest.

A series of horizontal black bars of varying lengths, with the longest bar at the bottom and the shortest at the top. This visual representation is used to indicate a list of items or steps, where the length of each bar corresponds to the size or importance of the item.

**ALLOB-DU1 - Clinical Study Protocol**

ALLOB-DU1\_CSP

V 05

Author: [name]

February 02, 2017

Pg. 69/136

**6.3 Tracking, Traceability, and Accountability of Investigational Medicinal Product**

A tracking system allowing complete traceability of both the Starting Materials (e.g., bone marrow) and IMP (i.e., ALLOB®) at all stages will be established and maintained (by Sponsor, Manufacturer, Managing Physician of the “Intermediary Structure”, Investigator and CRO). This tracking system would ensure that:

- The Starting Materials and IMP are tracked and traced during the whole process, from the eligibility and selection of the donor, through the donation, procurement, testing, processing, storage, preservation, labelling, packaging, release, transport, distribution, and delivery, to the implantation to the patient, each procedure and step being described in Standard Operating Procedures, and systematically collected, verified, and recorded using specific Forms and Receipts (and in the CRF).
- Production data of each batch are accurately tracked and recorded.
- There is also an accurate system in place to notify, report, investigate, register, and transmit information about any Serious Adverse Safety/Quality Events which may influence the quality and safety of the product, and which may be attributed to the procurement of starting material, testing, processing, storage, preservation, delivery, and distribution (see detailed description in Section 8).

In addition, it should be noted that all used syringes (without needles) will be kept and stored in each investigating site until monitor's verification visits, and destroyed after the monitoring visit on site and once the accountability is performed.

Finally, data and records required for full traceability will be kept by the Sponsor, Managing Physician of the Intermediary Structure, Manufacturer, and Investigator for a minimum of 30 years after clinical use.

ALLOB-DU1 - Clinical Study Protocol

ALLOB-DU1 CSP

V 05

Author: [name]

February 02, 2017

Pg. 70/136

## 7. SAFETY AND TOLERABILITY MEASUREMENTS AND ENDPOINTS

## 7.1 Overview of Safety Parameters and Endpoints

The safety and tolerability of the test product (ALLOB®) will be systematically investigated throughout the study period. Patients will be evaluated at each follow-up visit for the potential occurrence of any AE or SAE, related to either the product or the study procedures. Definitions of AE/SAE are in Section 8.

For the first 16 patients, recruitment will proceed stepwise by blocks of 4. Full first 2 weeks safety data of the first block of 4 patients will be analysed before the first patient of the second block will be treated. First 48 hours safety data of the second block of 4 patients will be analysed before treating the first patient of the next block. This latter scheme will be repeated until the 16th patient has been treated.

Table 6 below shows how the safety endpoints of this study relate to the study objectives. Assessments and measurements will be carried out at the times specified in the study Flow Chart (see above).

**Table 6: Overview of Safety Parameters and Timepoints**

## ALLOB-DU1 - Clinical Study Protocol

ALLOB-DU1_CSP	V 05	Author: [name]	February 02, 2017	Pg. 71/136
---------------	------	-------------	-------------------	------------

### 7.1.1 Vital Signs

**Blood pressure** (BP) will be assessed in all patients on site by standardised cuff measurements. Preferably, the same person will do all the measurements on the same patient.

Results of measurements should only be reported as AE if, in the Investigator's opinion, it is outside of "expected values or variations". Also they must be considered as SAE if it fulfils the SAE definition.

**Heart rate** will be measured once, in beats per minutes (bpm) after the patient has been in a resting state (seated) for at least 5 minutes. Heart rate will be counted for 30 seconds, multiplied by 2 and recorded in bpm.

The **Body temperature** and **Respiratory rate** will also be systematically measured.

